Study title: Quantitative Ultrasound with Velacur for Evaluation of Non-Alcoholic Fatty Liver Disease

PI: [name] MD

NCT 04576923

Document date: July 8, 2021

July 8, 2021

Quantitative Ultrasound with Velacur for Evaluation of Non-Alcoholic Fatty Liver Disease

Background

Nonalcoholic fatty liver disease (NAFLD) is the most common liver disease worldwide ¹. It is characterized by increased hepatic fat accumulation in the absence of significant alcohol intake. NAFLD has a wide spectrum that starts with simple accumulation of triglycerides droplets in hepatocytes (macrosteatosis) without associated inflammation, hepatocyte injury or fibrosis, a phenotype called non-alcoholic fatty liver (NAFL) ². A more severe NAFLD phenotype is nonalcoholic steatohepatitis (NASH), which in addition to the presence of macrosteatosis is characterized by hepatocyte ballooning, lobular inflammation with or without fibrosis. While NAFL generally has a benign course, NASH may progress to cause cirrhosis, liver failure and hepatocellular carcinoma (HCC) ^{3, 4}.

The global prevalence of NAFLD in the general population is estimated at 25% and it increases with age ¹. There is geographic variation in NAFLD prevalence probably due to differences in populations' genetic compositions, dietary habits and environmental aspects. About a quarter of the populations in Europe and North America are estimated to have NAFLD, whereas populations in South America and the Middle East are estimated to have the highest rates of NAFLD globally (range 30-32%)¹. NASH is estimated to affect 2% - 6% .of the general population, 7% - 30% of NAFLD patients who had a liver biopsy without a specific clinical indication (e.g. evaluation for liver organ donation), and 59% in NAFLD patients with clinical indication for liver biopsy (e.g. elevated liver enzymes) ¹.

Current NAFLD guidelines by the American Association of study of Liver Diseases (AASLD) do not recommend routine screening for NAFLD among patients with diabetes or obesity in the setting of primary care and obesity clinics ². Use of non-invasive clinical prediction models and detection methods such as vibration-controlled transient elastography by FibroScan® to evaluate the presence and severity of fibrosis is proposed ⁵. Several serum-based non-invasive clinical prediction models can be used to screen patients with NAFLD for NASH or advanced fibrosis ^{6, 7}. For example, the NAFLD fibrosis score (NFS) allows a non-invasive evaluation of the extent of fibrosis using weight, and age and laboratory data which include liver enzymes and serum glucose level ^{8, 9}. Another useful clinical tool to estimate fibrosis is Fibrosis-4 score which relies solely on laboratory data ¹⁰. When available, tools such as transient elastography (FibroScan®) with controlled attenuation parameter (CAP) allow simultaneous estimation amount of hepatic fat (using CAP) and fibrosis [using the liver stiffness measurement (LSM)] ^{5, 11}. MR based methods can also offer simultaneous assessment of hepatic fat and fibrosis, albeit it is not widely available and is more expensive ¹².

While the use of FibroScan® in liver clinics is attractive as a point of care exam that can provide immediate indirect data about hepatic steatosis and fibrosis in the clinic, advancement in quantitative ultrasound technology may now allow even more detailed and directed non-invasive assessment of these measures of liver disease.

July 8, 2021

Velacur offers the ability to simultaneously and noninvasively measure Attenuation Coefficient Estimate (ACE) as a quantitative measure of ultrasound attenuation¹³ and detection of hepatic steatosis in addition to LSM which measures deep volumetric liver elasticity using steady state shear waves, known as shear wave absolute viboelastography (SWAVE). This technology enables measurements of liver elasticity to a depth equal to the B-mode image, or in excess of 15 cm. The system consists of an ultrasound machine, a vibration device to excite shear waves in the patient and a ultrasound transducer. The vibration device induces shear waves in the liver at four different frequencies between 40Hz and 70Hz simultaneously. The ultrasound volume is acquired through the ribs at the same location as a typical transient elastography (TE) measurement. Volumes are collected in a fan of approximately 15 degrees and taken at a depth of 15cm, which much deeper than FibroScan® measurement (6 cm), and allows for much larger sample measurement (100,000 mm³) versus that measured by Fibroscan (3,140 mm^3).

Rationale and Specific Aims

Hypothesis and Specific Aims: *Velacur* with ACE and LSM measurements is a novel ultrasonic device that can estimate both liver steatosis and fibrosis using a sophisticated process. The availability of *Velacur* would allow a health care provider to make a diagnosis of NAFLD with or without advanced fibrosis quickly without a need for liver biopsy.

Hypothesis: The diagnosis and severity of NAFLD with or without advanced fibrosis can be defined using *Velacur*.

Specific Aims: To prospectively evaluate the utility of *Velacur* in assessing NAFLD with or without advanced fibrosis in patients seen in liver clinics for suspected NAFLD diagnosis.

Specific Aim #1: To prospectively evaluate the performance of *Velacur* for detecting hepatic steatosis and fibrosis in patients with suspected NAFLD by assessing correlation of ACE and LSM measured by *Velacur* to grade of steatosis and stage of fibrosis on liver histology of patients with NAFLD who undergo standard of care liver biopsy.

Specific Aim #2: To compare the performance of *Velacur* to that of FibroScan® in the same patient population to determine if either test is more accurate in correlating with NAFLD histology.

July 8, 2021

Specific Aim #3: To compare the performance of *Velacur* to that of non-invasive blood based markers such as APRI, FIB4, and NAFLD fibrosis score in predicting advanced fibrosis in biopsy proven NAFLD.

Proposed Study Design: The proposed study will evaluate the performance characteristics of LSM as a measure of fibrosis and ACE as a measure of hepatic steatosis by *Velacur* in patients with different stages of NAFLD. In addition, we will compare the diagnostic accuracy of ACE to CAP and LSM measured by *Velacur* to that measured by FibroScan® using liver histology as the reference standard. We will also compare the performance of these two methods to that of non-invasive blood based markers such as APRI, FIB4, and NAFLD fibrosis score in predicting advanced fibrosis in biopsy proven NAFLD.

Inclusion/Exclusion Criteria

Inclusion criteria:

- 1. Adults aged 18 years or older
- 2. History of biopsy proven NAFLD or NASH within 6 months prior to enrollment
- 3. Planned liver biopsy for evaluation of NAFLD within 6 months of enrollment
- 4. Suspected NAFLD or NASH with planned or recommended standard of care liver biopsy
- 5. Ability to provide informed consent

Exclusion criteria:

- 1. Fasting for less than three hours prior to the scan
- 2. Subject is a pregnant or lactating female
- 3. Subject with current, significant alcohol consumption or history of significant alcohol consumption for a period of more than 3 consecutive months any time within 1 year prior to screening. Significant alcohol consumption is defined as more than 20 gram per day in females and more than 30 grams per day in males, on average (a standard drink in the US is considered to be 14 grams of alcohol).
- 4. Subject is unable to reliably quantify alcohol consumption based upon local study physician judgment.
- 5. Subject uses drugs historically associated with NAFLD (amiodarone, methotrexate, systemic glucocorticoids, tetracyclines, tamoxifen, estrogens at doses greater than those used for hormone replacement, anabolic steroids, valproic acid, and other known hepatotoxins) for more than 2 weeks in the year prior to screening
- 6. Subject with history of cirrhosis and clinical evidence of hepatic decompensation as defined by the presence of any of the following abnormalities at screening:
 - a. Serum albumin less than 3.5 grams/deciliter (g/dL).
 - b. An INR greater than 1.5.
 - c. Total bilirubin greater than 2 milligrams per deciliter (mg/dL).
 - d. please note that people with compensated cirrhosis are not excluded from the study protocol
- 7. Subject has a history of bleeding esophageal varices, ascites or hepatic encephalopathy
- 8. Subject has history of other forms of chronic liver diseases such as viral hepatitis, autoimmune hepatitis, cholestatic liver disease (primary biliary cirrhosis or primary sclerosing cholangitis).
- 9. Subject with active substance abuse
- 10. Acute hepatitis defined as AST/ALT > 500 U/L
- 11. Patients with a pacemaker or defibrillator

12. Ascites

Enrollment/Randomization

Up to 100 patients will be seen at 3 different sites: Indiana University, Arizona Liver Institute, and Cedars-Sinai Medical Center.

Study Procedures

All patients have to be fasting for 3 hours prior to performance of the study. After subject identification and informed consent, measurement of liver stiffness with *Velacur* will be performed by a certified technician. At that time, subject participation in the protocol is complete. Duration of participation for the subject should be no more than one hour. Medical information from the subjects, including results of the laboratory and imaging tests, liver biopsy results and medical history will be collected from medical records and entered into a database. None of these tests would have been performed as part of this study, rather of as part of routine clinical care the patient receives. Laboratory data to calculate non-invasive blood based markers such as APRI, FIB4, and NAFLD fibrosis score generated within 6 months of the date of the liver biopsy will be collected. Additionally, slides from a standard of care liver biopsy will be made from the tissue collected during the biopsy and will be read centrally according to the NASH CRN system by an experienced pathologist. Digital slides will be created and read via artificial intelligence and the results of the readings will be added to the study database.

Reporting of Adverse Events or Unanticipated Problems Involving Risk to Participants or Others

Participation in this study may cause a loss of privacy. To minimize this risk, all of the patient's personal and medical data will be considered confidential to the extent allowed by law; every effort will be made to keep all of the information strictly confidential. All study information will be stored in locked cabinets and on password-protected computers. Only authorized personnel will have access to the samples, databases, and results. Samples will be labeled with a code. When the study is published, no names or other identifying information will be used.

While there are no direct risks from use of *Velacur*, patients may be uncomfortable lying on their back for a brief period of time. They may experience soreness at the probe site. There is a small risk of an allergic reaction to the gel utilized during the procedure.

Patients will be closely monitored for any evidence of adverse events. Any adverse events associated with the study will be documented and the IRB will be notified per reporting guidelines.

Given this is a minimal risk study, no Data Safety and Monitoring Board (DSMB) will be required.

Study Withdrawal/Discontinuation

Participants are free to withdraw from the study for any reason and at any time without giving a reason for doing so and without penalty or prejudice. The Investigator is also free to terminate a subject's involvement in the study at any time if the subject's clinical condition warrants it.

Statistical Considerations

Descriptive statistics such as mean, standard error, and percentages were used to characterize the cohort. Comparisons will be made between groups by using Student t test or analysis of variance. Pearson correlation coefficient will be used to detect the correlation between continuous variables. Multivariate analysis will be performed to examine the independent association between dependent and several independent variables. Sample size is based on clinical experience and precedent established for studies of similar design.

Privacy/Confidentiality Issues

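### Velacur's hypothesis is diagnostic, but the Aim 1 analysis names only tests of association and no measure of how well the device classifies patients

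*Protocol*

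**What the plan says.** **The claim.** Under Rationale and Specific Aims, the Protocol hypothesises that "The diagnosis and severity of NAFLD with or without advanced fibrosis can be defined using" Velacur. The lead-in says the device would let a provider reach the diagnosis "quickly without a need for liver biopsy".

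**The aim.** Specific Aim 1 sets out to evaluate Velacur's performance "by assessing correlation of ACE and LSM measured by" Velacur against the histological grade of steatosis and stage of fibrosis.

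**The design.** Proposed Study Design goes further than correlation. It undertakes to evaluate how stiffness performs as a measure of fibrosis and ACE as a measure of steatosis. It adds, for the comparison with FibroScan, that "we will compare the diagnostic accuracy of ACE to CAP and LSM measured by" Velacur with its FibroScan counterpart. It gives no accuracy measure, test or threshold for either purpose.

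**The methods.** Statistical Considerations has the same text in the Protocol and the SAP. After descriptive statistics it lists three inferential methods:
- for the link between two measurements, "Pearson correlation coefficient will be used to detect the correlation between continuous variables";
- for differences in level between sets of patients, "Comparisons will be made between groups by using Student t test or analysis of variance";
- for models with more than one explanatory factor, "Multivariate analysis will be performed to examine the independent association between dependent and several independent variables".

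Neither document mentions AUROC, sensitivity, specificity, a cut-off, a confidence interval, an alpha level or a success rule. On size, the Protocol says only "Up to 100 patients will be seen at 3 different sites".

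**The concern.** Saying that a device can define a diagnosis is a statement about sorting individual patients correctly. The usual null hypothesis of each listed test is zero correlation, equal means or no independent association. Rejecting such a null shows that readings differ on average between histology groups. It does not show how many patients would be put in the wrong group.

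The plan therefore states an accuracy purpose without a method that measures accuracy. It also says nothing about what result would support the hypothesis. Two things follow. A small p-value for a modest association could be presented as support for diagnosis without biopsy. Alternatively, an accuracy measure and a favourable benchmark could be chosen after the data are seen. A reader of the results could not tell from the plan whether either had happened.

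The point concerns Velacur's own claim under Aim 1. The comparisons with FibroScan and with blood markers are a separate matter: matching or beating a comparator would not by itself show that Velacur defines the diagnosis.

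**Working it through.** The plan gives no power, effect size or accuracy target, so there is no figure of its own to reproduce. The check asks how small an observed separation would already be significant under the listed tests.

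**Inputs.** From the Protocol: N of at most 100. Assumed here, because the documents do not state them:
- alpha 0.05, two-sided;
- normal readings with equal variance in the two groups;
- advanced fibrosis in 15% to 50% of patients;
- N=60 as an example of under-recruitment.

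**Pearson.** The smallest significant correlation is |r| = t / √(t² + N − 2).
- N=100: t = 1.984, so |r| = 0.197 and r² = 0.039, about 4% of variance.
- N=60: t = 2.002, so |r| = 0.254 and r² = 0.065.

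**t test, advanced fibrosis yes or no.** The smallest significant standardised difference is d = t × √(1/n₁ + 1/n₀). Under the normal model, AUROC = Φ(d/√2), and at the cut-off where the two are equal, sensitivity = specificity = Φ(d/2).

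Worked case, 30 against 70: √(1/30 + 1/70) = 0.2182; d = 1.984 × 0.2182 = 0.433; AUROC = Φ(0.306) = 0.620; sensitivity = specificity = Φ(0.217) = 0.586.

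| Advanced fibrosis | N=100: d | N=100: AUROC | N=60: d | N=60: AUROC |
|---|---|---|---|---|
| 15% | 0.556 | 0.653 | 0.724 | 0.696 |
| 20% | 0.496 | 0.637 | 0.646 | 0.676 |
| 30% | 0.433 | 0.620 | 0.564 | 0.655 |
| 40% | 0.405 | 0.613 | 0.527 | 0.645 |
| 50% | 0.397 | 0.611 | 0.517 | 0.643 |

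These are observed values at the edge of significance.

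**How often a weak device would get there (N=100, noncentral t).**
- True AUROC 0.62: p<0.05 in about 33% of studies at 15% prevalence, 50% at 30% and 57% at 50%.
- True AUROC 0.65: 58% with 20 advanced cases, 70% with 30 and 75% with 40.

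**What an interval would show.** With the Hanley-McNeil standard error at 30 against 70, an observed AUROC of 0.620 has SE 0.063. The 95% interval is 0.620 ± 1.96 × 0.063, or about 0.50 to 0.74. Reported this way, the same data could hardly be mistaken for a device that defines a diagnosis.

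**Illustration of a threshold.** For the lower limit to exceed 0.70 with 30 of 100 advanced, the observed AUROC must be about 0.80: at 0.803 the SE is 0.0524, and 0.803 − 1.96 × 0.0524 = 0.700. The required value is about 0.82 with 20 advanced cases and 0.795 with 40.

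**The case against.** The strongest reply is that the plan contains no decision rule at all. A reader might infer that, under the plan, a device with an AUROC near 0.62 would be declared to support the hypothesis. The documents do not support that. They state no alpha and no success criterion, and no sentence ties a significant test to the hypothesis. The fault is an absent criterion, not a lax one. The figure of 0.62 is also an observed value in one assumed case (30 against 70 at N=100). A device whose true AUROC was 0.62 would reach p<0.05 in only about half of such studies. With fewer patients the boundary rises, and at N=60 with 15% advanced fibrosis it is close to 0.70. All of this stands, and it is why the result is given as a range.

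A second reply is that Proposed Study Design does speak of performance and diagnostic accuracy. That is true, and it shows the intent to measure accuracy. But the section names no measure, and Statistical Considerations supplies none, so the intent has no analysis behind it.

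A third reply is that the remark about avoiding biopsy is motivation, and that a single-visit study with no stated confirmatory purpose need not set a pass/fail bar. This also stands. A reader might infer that a minimum AUROC such as 0.70 is required; nothing in the documents gives that or any other value. An estimate with its interval is enough to guard against over-claiming.

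None of these replies supplies a listed method that measures classification.

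**Conclusion.** The point holds as a mismatch between question and method. The hypothesis and the design section are diagnostic, while Aim 1 and the Statistical Considerations in both documents name only analyses of association. Followed as written, the plan would not produce the quantity needed to judge its own hypothesis, and it does not stop a weak association from being offered in its place.

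Under the assumptions listed in the working, significance on the t test begins at an observed AUROC of about 0.61 to 0.65 with 100 patients and about 0.64 to 0.70 with 60. The mismatch itself does not depend on those assumptions; only its size does.

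**What to change.** Add to Statistical Considerations in both documents, in wording such as: *The main analysis for Aim 1 is the AUROC, with 95% confidence interval, of Velacur LSM for advanced fibrosis and of ACE for one steatosis grade cut. Conclusions about the hypothesis rest on these estimates and intervals. A significant correlation or mean difference on its own is reported as an association, not as evidence of diagnosis without biopsy.*

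The text should also name the fibrosis stages that count as advanced, the steatosis cut and the confidence-interval method. One cut per reading does not cover the severity part of the hypothesis. Other cuts can be secondary, and conclusions about severity should be limited to the cuts actually analysed.

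If the sponsor wants a pass/fail claim, it should choose a minimum AUROC and fix it before scans are linked to histology. The 0.70 used in the working is only an example.

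**Cost.** A few sentences and slightly more analysis, with no new patients, procedures or data, since the scans and centrally read biopsies are already planned. The conclusion may be less favourable. If 0.70 were chosen, an observed AUROC of about 0.80 would be needed with 30 of 100 advanced. A device whose true AUROC was only at that level would clear the bar about half the time; one with a true AUROC of 0.85 would do so in about 84% of studies (Hanley-McNeil, same split).

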Study title: Quantitative Ultrasound with Velacur for Evaluation of Non-Alcoholic Fatty Liver Disease

PI: [name] MD

NCT 04576923

Statistical Considerations

Document date: July 8, 2021

Statistical Considerations

Descriptive statistics such as mean, standard error, and percentages were used to characterize the cohort. Comparisons will be made between groups by using Student t test or analysis of variance. Pearson correlation coefficient will be used to detect the correlation between continuous variables. Multivariate analysis will be performed to examine the independent association between dependent and several independent variables. Sample size is based on clinical experience and precedent established for studies of similar design.

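### Aim 2 is to decide whether Velacur or FibroScan is more accurate, but the plan fixes no primary comparison, significance level, histologic cut, reference read or paired-accuracy test

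*Protocol*

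**What the plan says.** Specific Aim 2 (Protocol, Rationale and Specific Aims) compares Velacur with FibroScan "in the same patient population to determine if either test is more accurate in correlating with NAFLD histology". The Proposed Study Design section makes this two contrasts: "we will compare the diagnostic accuracy of ACE to CAP and LSM measured by" Velacur against the FibroScan value, with histology as the reference. It then adds: "We will also compare the performance of these two methods to that of non-invasive blood based markers such as APRI, FIB4, and NAFLD fibrosis score". Specific Aim 3 is narrower. It sets Velacur alone against the same markers, and there the target is advanced fibrosis.

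The Statistical Considerations text is the same in the protocol and the SAP. On testing it says "Comparisons will be made between groups by using Student t test or analysis of variance" and "Pearson correlation coefficient will be used to detect the correlation between continuous variables", and it adds an unspecified multivariate analysis. Neither document gives a primary comparison, a significance level, a multiplicity rule or a test for a difference in accuracy between two tests done in the same patients.

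Under Study Procedures, biopsy results come from the medical record, a pathologist reads the slides centrally, and an artificial intelligence reading is added to the database. None of these is named as the reference for the comparison. On size, the Enrollment section says "Up to 100 patients will be seen at 3 different sites", and the stated basis is experience and precedent.

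**The concern.** Aim 2 ends in a verdict on two devices, but the plan leaves open what would count as that verdict. It could rest on steatosis or fibrosis, on any grade or stage cut, and on any of the reads. Advanced fibrosis is named as a target only for the blood-marker comparisons. Aim 2 refers to histology in general, which under Aim 1 means grade of steatosis and stage of fibrosis.

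The stated methods do not narrow this. A t test or ANOVA between groups compares sets of patients. A Pearson coefficient describes one device at a time. Neither, as described, tests whether one device is more accurate than another in the same patients. The deciding test would therefore be chosen after the data are in.

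With at most 100 patients, a chance difference between equally accurate devices could be reported as superiority, and a reader could not tell whether that comparison was the one meant to settle the question.

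**Working it through.** **No plan figure to reproduce.** The documents state no alpha, power or calculated sample size. Everything below assumes two-sided 0.05 per comparison and all tests truly equal.

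**Counting comparisons**
- Aim 2: ACE vs CAP, and Velacur LSM vs FibroScan LSM = 2.
- Aims 2 and 3 as worded: 2 + (Velacur × 3 named markers) = 5.
- Design text: 2 + (2 devices × 3 named markers) = 8. The marker list is introduced as examples, so it is open-ended.

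**If independent:** P(at least one false difference) = 1 − 0.95^k.
- k = 2: 1 − 0.9025 = 9.75%
- k = 5: 22.6%
- k = 8: 33.7%
- Upper bound for k = 8 under any dependence: 8 × 0.05 = 40%

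**Allowing for dependence.** The comparisons share patients, reference standard and tests. A Monte Carlo run (1,000,000 draws per setting) gave the five fibrosis tests (two LSMs, APRI, FIB4, NAFLD fibrosis score) correlated accuracy estimates of equal variance. It tested the planned pairs and added ACE vs CAP as an independent test. The correlations are assumed.

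| Device–device / marker–marker / device–marker correlation | 8 comparisons | 5 comparisons |
|---|---|---|
| 0 / 0 / 0 | 27.1% | 19.7% |
| 0.3 / 0.3 / 0.3 | 27.2% | 19.9% |
| 0.6 / 0.5 / 0.3 | 25.0% | 19.4% |
| 0.7 / 0.6 / 0.4 | 24.5% | 19.4% |
| 0.8 / 0.7 / 0.3 | 22.2% | 18.6% |
| 0.8 / 0.8 / 0.3 | 20.9% | 17.6% |
| 0.9 / 0.9 / 0.3 | 18.7% | 16.7% |

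Together with the independent case, this gives about 19–34% for eight and about 17–23% for five. The two Aim 2 comparisons stay near 10% throughout.

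**Aim 2 alone with the cuts left open.** This was simulated with N = 100, both devices truly equal, paired DeLong tests, between-device error correlation from 0 to 0.9, and balanced or skewed stage distributions (2,000 data sets per setting). One fixed cut for each measure gave 8–10%. Testing three steatosis cuts and four fibrosis cuts gave 25–32%, and a separate check gave 26–33%. The seven cuts are an assumption, since the documents list none. A little of the excess may come from DeLong's behaviour in small groups. The range is approximate, and very strong correlation between devices pulls it towards or slightly below its lower end.

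**The case against.** A reader might infer that all eight comparisons feed the question of which device is more accurate, so that the chance of a false winner exceeds one in four. The documents do not support that. Aim 2 concerns two devices and two comparisons, about 10% with one cut each. The six marker comparisons cannot show which device is better, and three of them do not involve Velacur. Aim 3 as worded brings the total to five, not eight. For the eight, a figure above one in four also needs weak or equal correlation among tests; with stronger within-class correlation it falls to 19–22%.

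A reader might likewise count 3 + 4 + 6 = 13 tests and quote 1 − 0.95^13 = 49%. That treats adjacent thresholds, which reuse the same scores in the same patients, as independent, and the plan does not list those threshold analyses.

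It is also fair to say that steatosis and fibrosis are separate questions, so adjusting across them is a choice, and that the work may be meant as exploratory. The first point stands and shapes the fix. On the second, neither document says so, and Aim 2 is worded as a determination.

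What these objections leave untouched is the gap itself. The 10% figure holds only if one cut per measure is fixed in advance, and the plan fixes none for Aim 2.

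**Conclusion.** The concern holds in limited form. Aim 2 is a decision aim without a named deciding comparison, significance level, cut, reference read or paired-accuracy test.

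The size depends on how the gap is filled. It is about 10% with one fixed cut per measure, and about a quarter to a third (25–33%) within Aim 2 alone if seven cuts are tested. If every comparison in the design text is treated as a claim, it is about 19–34%; for Aims 2 and 3 as worded it is about 17–23%.

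All of these rest on an assumed two-sided 0.05 and truly equal tests. The 25–33% also rests on the assumed cuts, and the lower ends of the last two ranges on assumed correlations. The recommendation is the same anywhere in these ranges. This should be changed before the data are analysed. It does not put the data collection at risk.

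**What to change.** Add to the SAP:

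- The primary Aim 2 comparisons are (1) Velacur LSM vs FibroScan LSM for advanced fibrosis and (2) ACE vs CAP at one steatosis threshold named in advance. Each is a paired AUROC difference (DeLong) with a 95% CI, against the central pathologist read.
- State whether the two are separate questions, each at two-sided 0.05, or share 0.05, for example by Holm. Either can be defended, but it must be stated beforehand.
- Other thresholds, the artificial intelligence read and the blood-marker comparisons are secondary. They are reported as paired differences with 95% CIs and without multiplicity-controlled claims.
- Reconcile Aim 3 with the design text on whether FibroScan is also compared with the markers.

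This costs wording only, with no extra patients or measurements. If the two primaries share alpha, the smaller p-value is judged at 0.025 (0.05/2), so some power is lost. The secondary comparisons, including those serving Aim 3, carry less weight. Whether Aim 3 should keep a formal claim is for the investigators to decide; if so, it needs its own named comparison and alpha.
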